Are there any procedures involved in this protocol that will be performed at YNHH or one of its affiliated entities?

Yes No

If Yes, please answer questions a through c and note instructions below.

a. Does your YNHH privilege delineation currently include the specific procedure that you will perform? Yes

No

b. Will you be using any new equipment or equipment that you have not used in the past for this procedure? Yes

No

c. Will a novel approach using existing equipment be applied? Yes No

If you answered "no" to question 4a, or "yes" to question 4b or c, please contact the YNHH Department of Physician Services ([name]) for prior approval before commencing with your research protocol.

IMPORTANT REMINDER ABOUT RESEARCH AT YNHH

Please note that if this protocol includes Yale-New Haven Hospital subjects, including subjects at the HRU, the Principal Investigator and any co-investigators who are physicians or mid-level practitioners (includes PAs, APRNs, psychologists and speech pathologists) who may have direct patient contact with subjects on YNHH premises must have medical staff appointment and appropriate clinical privileges at YNHH. If you are uncertain whether the study personnel meet the criteria, please telephone the Physician Services Department at [contact]. By submitting this protocol as a PI, you attest that you and any co-investigator who may have patient contact has a medical staff appointment and appropriate clinical privileges at YNHH.

Data and Safety Monitoring Plans (DSMP) 420
FR.1

Greater Than Minimal Risk DSMP

1. Personnel responsible for the safety review and its frequency:

The principal investigator will be responsible for monitoring the data, assuring protocol compliance, and conducting the safety reviews at the specified frequency, which must be conducted at a minimum of every 6 months (including when reapproval of the protocol is sought). During the review process, the principal investigator (monitor) will evaluate whether the study should continue unchanged, require modification/amendment, or close to enrollment. Either the principal investigator, the IRB and Safety Monitoring Committee (DSMC) have the authority to stop or suspend the study or require modifications.

2. The risks associated with the current study are deemed greater than minimal for the following reasons:

1. We do not view the risks associated with the use of stable isotopes as minimal risks.

Although we have assessed the proposed study as one of greater than minimal risk, the potential exists for anticipated and/or unanticipated adverse events, serious or otherwise, to occur since it is not possible to predict with certainty the absolute risk in any given individual or in advance of first-hand experience with the proposed study methods. Therefore, we provide a plan for monitoring the data and safety of the proposed study as follows:

3. Attribution of Adverse Events:

Adverse events will be monitored for each subject participating in the study and attributed to the study procedures / design by the principal investigator (*[name]*) according to the following categories:

- a.) Definite: Adverse event is clearly related to investigational procedures(s)/agent(s).
- b.) Probable: Adverse event is likely related to investigational procedures(s)/agent(s).
- c.) Possible: Adverse event may be related to investigational procedures(s)/agent(s).
- d.) Unlikely: Adverse event is likely not to be related to the investigational procedures(s)/agent(s).
- e.) Unrelated: Adverse event is clearly not related to investigational procedures(s)/agent(s).

4. Plan for Grading Adverse Events:

The following scale will be used in grading the severity of adverse events noted during the study:

1. Mild adverse event
2. Moderate adverse event
3. Severe

5. Plan for Determining Seriousness of Adverse Events:

Serious Adverse Events:

In addition to grading the adverse event, the PI will determine whether the adverse event meets the criteria for a Serious Adverse Event (SAE). An adverse event is considered serious if it results in any of the following outcomes:

1. Death;
2. A life-threatening experience in-patient hospitalization or prolongation of existing hospitalization;
3. A persistent or significant disability or incapacity;
4. A congenital anomaly or birth defect; OR
5. Any other adverse event that, based upon appropriate medical judgment, may jeopardize the subject's health and may require medical or surgical intervention to prevent one of the other outcomes listed in this definition.

An adverse event may be graded as severe but still not meet the criteria for a Serious Adverse Event. Similarly, an adverse event may be graded as moderate but still meet the criteria for an SAE. It is important for the PI to consider the grade of the event as well as its "seriousness" when determining whether reporting to the IRB is necessary.

6. Plan for reporting UPIRSOs (including Adverse Events) to the IRB

The principal investigator will report the following types of events to the IRB:

Any incident, experience or outcome that meets **ALL 3** of the following criteria:

1. Is unexpected (in terms of nature, specificity, severity, or frequency) given (a) the research procedures described in the protocol-related documents, such as the IRB-approved protocol and informed consent document and (b) the characteristics of the subject population being studied; AND
2. Is related or possibly related to participation in the research (*possibly related* means there is a reasonable possibility that the incident, experience, or outcome may have been caused by the procedures involved in the research); AND
3. Suggests that the research places subjects or others at greater risk of harm (including physical, psychological, economic, legal, or social harm) than was previously known or recognized.

Unanticipated Problems Involving Risks to Subjects or Others (UPIRSOs) may be medical or nonmedical in nature, and include – but are not limited to – *serious, unexpected, and related adverse events and unanticipated adverse device effects*. **Please note** that adverse events are reportable to the IRB as UPIRSOs **only** if they meet all 3 criteria listed above.

These UPIRSOs/SAEs will be reported to the IRB in accordance with IRB Policy 710, using the appropriate forms found on the website. All related events involving risk but not meeting the *prompt*

reporting requirements described in IRB Policy 710 should be reported to the IRB in summary form at the time of continuing review. If appropriate, such summary may be a simple brief statement that events have occurred at the expected frequency and level of severity as previously documented. In lieu of a summary of external events, a current DSMB report can be submitted for research studies that are subject to oversight by a DSMB (or other monitoring entity that is monitoring the study on behalf of an industry sponsor).

The DSMB is composed by:

- 1) [name]. Professor of Pediatrics at Yale University. [name] is an expert of type 1 diabetes and has participated to several clinical trials studying the efficacy of closed loop system in children with type 1 diabetes.
- 2) [name]. Associate Professor of Pediatrics at Yale University. [name] has a longstanding expertise in the pharmacokinetic properties of insulin analogues in type 1 diabetes. The PI will report to DSMB every 6 months by conference call and every year by in person meeting. Unscheduled meetings will be arranged in case any events should occur. The PI will provide the data obtained from the study and the potential adverse events reported by the patients. The DSMB will review the data and provide report the findings to the PI by email or in person meeting. The DSMB will be responsible for reviewing comprehensive, cumulative, unblinded safety reports, and employing stopping rules if there is evidence of differential effects in either risk or benefit.

7. Plan for reporting adverse events to co-investigators on the study, as appropriate the protocol's research monitor(s), e.g., industrial sponsor, Yale Cancer Center Data and Safety Monitoring Committee (DSMC), Protocol Review Committee (PRC), DSMBs, study sponsors, funding and regulatory agencies, and regulatory and decision-making bodies.

For the current study, the following individuals, funding, and/or regulatory agencies will be notified:

- All Co-Investigators listed on the protocol.
- National Institutes of Health
- Data Safety Monitoring Board (DSMB)

The principal investigator (*[name]*) will conduct a review of all adverse events upon completion of every study subject. The research participant will also be given a study safety questionnaire at the end of the study that asks about the degree to which they experienced any side effects. The principal investigator will evaluate the frequency and severity of the adverse events and determine if modifications to the protocol or consent form are required.

Please note: For any study that may be considered high risk, the IRB will be more focused on the safety requirements for the study and a DSMB will likely be required.

*For more guidance on Adverse Event reporting and DSMPs, see **IRB Policy 710 Reporting Unanticipated Problems Involving Risks to Subjects or Others, including Adverse Events***

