
When possible, the MRI scan will be on the same day as the OGTT as noted above, however it can be scheduled on a different day (either prior to or following completion of OGTT) based on ease of scheduling for the patient.

Aim 1: Determine whether the gut microbiota of obese adolescents have greater ability to ferment carbohydrates

(CHO) and synthesize SCFA compared to the microbiota of lean subjects, therefore obtaining a higher metabolizable energy yield from an equal amount of dietary CHO. *Hypothesis: For an equal amount of dietary CHO, obese youth will synthesize SCFA at higher rates than lean youth.*

All subjects will be instructed about the benefit of a healthy diet and will meet with the dietitian who will advise on healthy feeding behavior and lifestyle and will be given the option of enrolling, free of charge, in the Yale Pediatric Weight Management Program called “Bright Bodies.” The program includes the following components: exercise, nutrition education, behavior modification, and psychosocial support.

We will enroll an equal number of obese (100) and lean (100). Lean adolescents will be recruited if at risk of developing obesity, prediabetes or diabetes due to their family history. The dietitian will instruct the subjects to follow a 3-day pre-intervention meal plan to ensure standardized calories and macronutrients intake up to the day of investigation in amounts to maintain weight in both groups. The pre-intervention diet will be based on the subjects’ age, weight and usual intake. The subjects will be admitted at the Hospital Research Unit (HRU) of the

[figure not shown]
Yale New Haven Hospital at 7.00 AM. To determine SCFA synthetic rates we will give orally 20g of lactulose, an oligosaccharide naturally present in nature that is extracted from chicory. To account for hepatic uptake, isotope exchange in the TCA cycle in the liver

and endogenous production by the liver, deuterated-SCFA will be infused from 7.30 AM, this will allow us to reach the quasi steady state for 2H-SCFA after ~1 hour. We will infuse 0.7 micromol/kg/min of labeled acetate after a labeled acetate priming dose of 1 mg/Kg. To assess SCFA synthesis blood samples will be collected every hour until 6.00 pm for a total of 150 ml (Figure 1). The subjects will be allowed to drink during the study, a meal will be served at the end of the study.

[figure not shown]

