Hypothesis: Lowering the amount of dietary CHO will shift the composition of the gut microbiota towards species with a lower ability to ferment carbohydrates and synthesize SCFA. Twenty-six obese subjects will be enrolled in a cross-over study and challenged with a low CHO or a normal CHO diet for a week. The subjects will switch diet after 4 weeks washout. Stool samples will be collected before and after the intervention to evaluate the gut microbiota. SCFA synthesis (as described in aim 1) will be measured at the beginning and at the end of the diet. Subjects will be enrolled after a 3 days run in period, in which they will try whether they could follow a low carbohydrates diet.

Dietary intervention.

a) Dietary Composition: The control “standard” diet composition will follow the American Dietary Guidelines of 55% CHO, 15% pro, and 30% fat. CHO content will be primarily complex CHO of high quality (14 g fiber/1,000 kcals and <10% of total kcals in the form of sugar). Fat content will be <7% saturated fats and primarily consist of monounsaturated fats. The experimental diet will consist of 30% CHO, 35% pro, and 35% fat. Since the experimental diet is lower in CHO, the fiber and sugar content will be calculated based on total CHO in the same percentage as the control (0.25 g fiber per each kcal of CHO and 18.2% sugar for total CHO). This will ensure the same quality of CHO in both diets (for example, <10% of total kcals from sugar would be a higher sugar intake in the low CHO diet). Kcal levels will be determined based on subject’s usual food intake. The subjects will be instructed to keep a 3-day food record (2 weekdays and 1 weekend day) prior to the study and the average kcal intake will be calculated using the Nutrition Data Systems for Research (NDSR) (University of Minnesota, 2016 version). Kcal levels will be assigned to the closest 200 kcals (1800, 2000, 2200, 2400, 2600, 2800, 3000). Utilizing the formulas to derive the same quality of CHO in both the standard- and low-CHO diets, the 2000 kcal standard diet, for example, will consist of 1100 kcals of CHO (55% total kcals), 27 g fiber (.025 g fiber per each kcal of CHO), and 50 g sugar (18.2% total CHO), while the low-CHO diet will consist of 600 kcals of CHO (30% total kcals), 15 g fiber (.025 g fiber per each kcal of CHO), and 27 g sugar (18.2% total CHO). A 3-day rotating menu will be

provided for both groups to ensure variety and increase compliance.

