The labeled glucose is prepared by the Investigational Drug Service of the Yale Pharmacy, as a solution of 20% (w/v) in water. The labeled glucose is infused following a protocol used for decades in the Yale Magnetic Resonance Research Center (MRRC), consisting of a ramp phase followed by a plateau phase. The amount of glucose infused is 0.75g/kg body weight (BW); the volume of glucose solution infused over a 120 min study is 3.6 ml/kg BW.

TCA cycle measurement in the liver.

To measure TCA cycle measurement in the liver we will infuse d3-acetate for 2 hours and we will detect the changes in TCA derived compounds in the liver during the infusion. A total of 50 ml of blood will be obtained during this study.

The labeled acetate is prepared by the Investigational Drug Service of the Yale Pharmacy, as a solution of 350 mM 2H-labeled sodium-acetate in water. The labeled acetate is infused following a protocol used for decades in the Yale MRRC, consisting of a ramp phase followed by a plateau phase. The amount of acetate infused is 0.73g/kg body weight (BW); the volume of acetate solution infused over a 120 min study is 14.2 ml/kg BW.

Calendar of activities for each aim (visits, frequency, assessments, blood draw collection, week number).

Visit number	Frequency	Assessment	Amount of blood to be collected	Week number
AIM 1				
1	once	OGTT	120	1
2	once	Acetate synthesis	94	2
AIM 2				
1	once	DNL assessment	150	3
AIM 3				
1	once	Acetate synthesis	94	4
2	once	Acetate synthesis	94	5
3	once	Acetate synthesis	94	6
4	once	Acetate synthesis	94	7
AIM 4				
1	once	One year follow-up	0	8
AIM 5				
1	once	gluconeogenesis	150	9
AIM 6				
1	once	MRI/Infusion - Brain	50	10
2	once	MRI/Infusion - Liver	50	11

Each visit is one day. If a subject is recruited for more than one aims, then at least 12 weeks will be allowed between the visits

5. Genetic Testing

The genetics portion of the study is optional. Subjects who do not wish to have additional blood drawn for genetic analysis may still have the OGTT. We may wish to contact family members of the subject for the genetic study as well. However, no family member will be contacted without the permission of the index subject, and

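### The blood volume for one SCFA (acetate) synthesis visit is 150 ml in the procedure text but 94 in the calendar, a gap of up to 224 ml over the four Aim 3 visits

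*Combined protocol and SAP*

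**What the plan says.** Three places in Section I, item 4 (Research Plan) bear on this point.

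- **Aim 1 procedure.** After oral lactulose and during the labeled acetate infusion, "blood samples will be collected every hour until 6.00 pm for a total of 150 ml (Figure 1").
- **Aim 3 procedure.** The text gives no volume of its own. It refers back to Aim 1: "SCFA synthesis (as described in aim 1) will be measured at the beginning and at the end of the diet". The design is a two-period cross-over, so this means four measurements per participant.
- **Calendar of activities.** The visit appears as "Acetate synthesis". The Aim 1 row reads "Acetate synthesis 94 2". The four Aim 3 rows read "Acetate synthesis 94 4", "Acetate synthesis 94 5", "Acetate synthesis 94 6" and "Acetate synthesis 94 7". In each row the middle number is the blood volume and the last is the week. The blood column has no unit.

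A note under the calendar requires at least 12 weeks between visits for anyone recruited to more than one aim. Section I, item 8 (Inclusion/Exclusion Criteria) sets the age range at 15 to 25 years and excludes a hematocrit below 32%. It also has hematocrit measured at the research unit on the day, before the study starts; the study goes ahead only if the value is above 32% and no anemia symptoms are reported.

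**The concern.** The same procedure carries two blood volumes, and nothing in the documents explains the difference. The volume drawn is a safety figure. Participants may be as young as 15. Item 12 rates the study as greater than minimal risk overall and, for children, as a minor increment over minimal risk without prospect of direct benefit. The risk section (item 10) states no blood volume, so a reader who wants the exposure must take it from the procedure text or the calendar, and they disagree.

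Aim 3 is where this counts most, because each of its 26 planned participants has the procedure four times. The 12-week spacing rule covers people who join more than one aim and does not separate the visits within Aim 3.

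**Working it through.** **1. Are these the same visit?** The Aim 1 study measures SCFA synthesis with a labeled acetate infusion. The Aim 6 text describes labeled acetate as the compound in use for acetate production in Aims 1 and 3. The calendar has one acetate synthesis visit in Aim 1 and four in Aim 3. The Aim 3 text implies 2 measurements per diet × 2 diets = 4. The counts agree, so the calendar rows are the visits that the text describes.

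**2. Is the calendar in ml?** Compare its other blood volumes with the procedure text:

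| Visit | Calendar | Procedure text |
|---|---|---|
| OGTT | 120 | 120 cc |
| Aim 2, de novo lipogenesis | 150 | 150 ml |
| Aim 5, gluconeogenesis | 150 | 150 ml |
| Aim 6, brain | 50 | 50 ml |
| Aim 6, liver | 50 | 50 ml |
| Acetate synthesis (Aim 1; Aim 3 by reference) | 94 | 150 ml |

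All the others agree in ml or cc. Only the acetate rows differ, and the same 94 appears in all five of them, so an isolated slip in one row is not the explanation.

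**3. Gap per visit.** 150 − 94 = 56 ml. That is 56/94 = 60% of the calendar figure, or 56/150 = 37% of the text figure.

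**4. Aim 3.** Text: 4 × 150 = 600 ml. Calendar: 4 × 94 = 376 ml. Gap: 4 × 56 = 224 ml. This is a maximum, because 150 ml reaches Aim 3 only through the reference to Aim 1.

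**5. Aim 1 (OGTT plus one acetate visit).** Text: 120 + 150 = 270 ml. Calendar: 120 + 94 = 214 ml. Gap: 56 ml.

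**6. A participant in Aims 1 and 3.** Text: 120 + 5 × 150 = 870 ml. Calendar: 120 + 5 × 94 = 590 ml. Gap: 5 × 56 = 280 ml, with the 12-week rule applying between the aims.

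**7. Time span of Aim 3.** The Aim 3 text has two one-week diets with a four-week washout between them: 1 + 4 + 1 = about 6 weeks.

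**8. Does the sampling schedule decide it?** Hourly samples from about 7 or 8 AM to 6 PM give 11 or 12 draws. For 150 ml that is 150/12 = 12.5 to 150/11 = 13.6 ml per draw. For 94 ml it is 94/12 = 7.8 to 94/11 = 8.5 ml per draw. The documents state no volume per draw, so either total is compatible with the schedule.

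**The case against.** The best case for leaving this alone has two parts. First, if 150 ml is the outdated or rounded-up figure, the narrative already discloses the larger volume and nobody is bled more than it says. Second, the hematocrit and symptom check on the day works whichever volume is used. Both points stand as limits on the seriousness. Neither removes the contradiction, since the check does not tell a reviewer or a family how much blood will be taken.

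A reader might also infer more than the documents support:

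- **That the calendar understates the true draw.** Nothing shows 150 ml to be the correct figure. The error could lie in either place.
- **That the Aim 3 blood is taken within four weeks.** The calendar numbers those visits as weeks 4 to 7, but this conflicts with the four-week washout. The week column runs straight from 1 to 11 and puts a one-year follow-up at week 8, so it reads as a sequence number and not as elapsed time.
- **That one person may give 1,270 ml against a listed 990 ml.** These are correct sums over every listed visit: 120 + 150 + 150 + 600 + 0 + 150 + 50 + 50, and the same with 94 for each acetate visit. But they assume one person in every aim, which the plan nowhere says will happen, and the 12-week rule would spread those visits well beyond the 11 weeks listed.
- **That an approved limit is exceeded or consent is wrong.** The documents state no limit on blood volume, and the consent forms were not available for this check.

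**Conclusion.** The inconsistency is real: two current parts of the plan give different blood volumes for one procedure, and at least one must be wrong. The size is 56 ml per visit and up to 224 ml over the four Aim 3 visits (600 against 376 ml), spread over about six weeks. The direction is unknown.

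This rests on two assumptions: that the calendar is in ml, which its other blood volumes support, and that the reference in Aim 3 to the Aim 1 procedure carries the blood volume with it. Participants are aged 15 to 25, so the point is not confined to adolescents, although the youngest are the reason to settle it. It is worth correcting because it concerns participant safety and costs little. It does not bear on any estimate, test or sample size.

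**What to change.** Reconcile the Aim 1 procedure, the Aim 3 procedure and the calendar to one volume per acetate synthesis visit; the sponsor must determine which figure applies. State the volume explicitly in the Aim 3 text as well as by reference, and print the unit in the calendar's blood column. Restate the cumulative volume for Aim 3 and for participants who join more than one aim, noting the 12-week spacing beside the latter. Check that any other study document that gives the volume, consent forms included, carries the same figure.

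The cost is an amendment to wording. No analysis, sample size or endpoint definition changes.

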We will also collect the breath hourly hydrogen breath test during the study to assess colonic fermentation by measuring hydrogen in the breath. Subjects blow into a small box to collect the breath. There are no risks related to this test.

Rationale for using lactulose as substrate to measure SCFA synthesis. In order to study the ability of the gut microbiota to ferment carbohydrates, we have chosen lactulose because the SCFA synthesis and kinetics arising from lactulose ingestion has been widely studied and is well known. Due to the structural conformation of its linkages, lactulose resists hydrolysis in the human small intestine and is almost completely fermented by the colonic microbiota. Lactulose has low osmotic activity, however it may cause uncomfortable bowel movements, flatulence, loose stools, bloating, cramps, and diarrhea.

Aim 1 Follow-up: After the completion of Aim 1, participants will be invited back for a one-year follow-up to measure height, weight, body mass composition with the Tanita scale, and to collect a 3-day food log. This follow-up is to assess if acetate production predicts change in BMI and body composition one year post study.

Aim 2: Determine whether the SCFA synthetic rates modulate hepatic de novo lipogenesis. Hypothesis: High rates of SCFA synthesis enhance hepatic de novo lipogenesis. Subjects will assume 3ml/ Kg of body water of D2O in three doses *per os* (at 7:00 PM, 10:00 PM and 3:00 AM) the night before the study. At the test day at 7:30 AM they will consume 2g of ¹³C Inulin, 13g of unlabeled inulin. Blood draws will be taken every hour until 8:00 PM. The total blood to be drawn is about 150 ml. The subjects will be allowed to drink during the study, a meal will be served at the end of the study.

[figure not shown]
We will also collect the breath hourly hydrogen breath test during the study to assess colonic fermentation by measuring hydrogen in the breath. Subjects blow into a small box to collect the breath. There are no risks related to this test.

Aim 3: Test the effect of an isocaloric low carbohydrate (CHO) diet on the bacterial synthesis of SCFA.

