Statistical plan for aim 6. Sample size was estimated with the clinicalcalc online software ([Sample Size Calculator \(clinicalcalc.com\)](https://www.clinicalcalc.com)). Since lactate serves as a precursor of TCA cycle, we based our power calculations on the lactate levels measured during the fasting state in 12 lean and 18 obese children. Based on the mean+/-SD of lactate levels in non-obese group of 0.78+/-0.22 and in the group with obesity 1.023 +/- 0.36, a sample size of 23 subjects per group (46) is needed for an alpha of 0.05 and a power of 95%. Statistical Analyses: Median and interquartile ranges will be calculated. The primary outcome will be TCA cycle after 6,6 D glucose ingestion during the steady state. Non-parametric two sided test will be used to compare TCA cycle between the groups.

SECTION II: RESEARCH INVOLVING DRUGS, BIOLOGICS, RADIOTRACERS, PLACEBOS AND DEVICES

If this section (or one of its parts, A or B) is not applicable, check off N/A and delete the rest of the section.

A. RADIOTRACERS N/A

B. DRUGS/BIOLOGICS N/A

Does the study do any of the following:

Specify the use of an approved drug or biologic?

Use an unapproved drug or biologic?

Use a food or dietary supplement to diagnose, cure, treat, or mitigate a disease or condition? No

This study uses:

13C inulin (labeled) (isotope)
deuterated SCFA/labeled acetate
Deuterium labeled water (heavy water D2O)
6,6-2H2-glucose (isotope)

Lactulose is a dietary supplement that is approved to treat constipation. We will use lactulose to stimulate production of short chain fatty acids by the gut flora.

Cold Isotopes:

FDA allows the use of cold isotopes in research without an IND when certain conditions apply (see below). Confirm that the following are true:

1. *The research is intended to obtain basic information regarding the metabolism (including kinetics, distribution, and localization) of a drug labeled with a cold isotope or regarding human physiology, pathophysiology, or biochemistry.*
2. *The research is not intended for immediate therapeutic, diagnostic, or preventive benefit to the study subject.*
3. *The dose to be administered is known not to cause any clinically detectable pharmacologic effect in humans based on clinical data from published literature or other valid human studies.*
4. *The quality of the cold isotope meets relevant quality standards.*

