5. *The investigation [will be] conducted in compliance with the requirements for review by an IRB (21 CFR part 56) and the requirements for informed consent (21 CFR part 50).*

I confirm all of the 5 points above. In fact, the study is intended to obtain basic information regarding the metabolism, not to provide therapeutic or diagnostic benefit.

The dose of isotopes to be used have been shown to be safe. In particular, D2O and 13C inulin have shown to be safe at the dose that we are providing. We and others used D2O at the proposed dose in previous studies without any side effects (Goffredo M et al. JCEM 2017). For the 13C inulin other investigators have used up to 15grams of labeled Inulin without any side effect (Deroover L et al. Nutrients 2017).

1. If an exemption from IND filing requirements is sought for a clinical investigation of a drug product that is lawfully marketed in the United States, review the following categories and complete the category that applies (*and delete the inapplicable categories*):

Exempt Category 1: The clinical investigation of a drug product that is lawfully marketed in the United States

can be exempt from IND regulations if all of the following are yes:

1. The intention of the investigation is NOT to report to the FDA as a well-controlled study in support of a new indication for use or to be used to support any other significant change in the labeling for the drug.	
---	-------------------------------------

2. The drug that is undergoing investigation is lawfully marketed as a prescription drug product, and the intention of the investigation is NOT to support a significant change in the advertising for the product.	
3. The investigation does NOT involve a route of administration or dosage level or use in populations or other factor that significantly increases the risks (or decreases the acceptability of the risks) associated with the use of the drug product	
4. The investigation will be conducted in compliance with the requirements for institutional (HIC) review and with the requirements for informed consent of the FDA regulations (21 CFR Part 50 and 21 CFR Part 56).	
5. The investigation will be conducted in compliance with the requirements regarding promotion and charging for investigational drugs.	

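### The acetate concentration, volume and mass given for the Aim 6 liver infusion do not agree, and the Risks text conflicts with the procedures on D2O dose and isotope route

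*Combined protocol and SAP*

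**What the plan says.** **Acetate, Aim 6 (Section I, item 4, TCA cycle measurement in the liver).** The route and duration are given as "To measure TCA cycle measurement in the liver we will infuse d3-acetate for 2 hours". The pharmacy prepares the tracer "as a solution of 350 mM 2H-labeled sodium-acetate in water". The dose is then given twice, by mass and by volume: "The amount of acetate infused is 0.73g/kg body weight (BW); the volume of acetate solution infused over a 120 min study is 14.2 ml/kg". The sodium salt is named. Whether the mass refers to the anhydrous salt, a hydrate or the acetate ion is not.

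**Acetate elsewhere.** The only other acetate dose is in Aim 1, whose method Aim 3 reuses: "We will infuse 0.7 micromol/kg/min of labeled acetate after a labeled acetate priming dose of 1 mg/Kg". That is a different infusion.

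**D2O.** The procedures for Aim 2 and Aim 5 agree: "Subjects will assume 3ml/ Kg of body water of D2O in three doses". Section I, item 10 (Risks) instead gives a range of 1 to 2 mg per kg of weight.

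**Route.** In Section I, item 11 (Minimizing Risks), one sentence says that oral administration removes any infection risk from isotope infusion. The next two sentences speak of isotope infusions in earlier studies and of acetate infusion in this one.

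**Cold-isotope conditions (Section II, part B).** Condition 3 reads "The dose to be administered is known not to cause any clinically detectable pharmacologic effect in humans", and the investigator writes "I confirm all of the 5 points above". After a general statement that the isotope doses are safe, the text continues: "In particular, D2O and 13C inulin have shown to be safe at the dose that we are providing".

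**The concern.** Concentration, volume and mass are tied by one equation, so any two of them fix the third. Here the third does not follow. A reader therefore cannot tell from the protocol how much acetate is planned per kilogram. The D2O dose has the same problem across sections, with a difference of orders of magnitude rather than a few per cent.

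These are dose and risk figures for compounds given to participants aged 15 to 25, in a study that the investigator rates as greater than minimal risk because of the stable isotopes. The cold-isotope confirmation concerns the dose to be administered. If the protocol gives that dose in two ways that disagree, it is unclear which dose was confirmed.

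**Working it through.** **1. Acetate: can the stated 0.73 g/kg be reproduced?**

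Inputs from the Aim 6 liver text: 350 mM (0.350 mmol/ml), 14.2 ml/kg, 0.73 g/kg. Molar masses are not in the documents; I assume standard atomic masses: d3-acetate ion 62.06, sodium d3-acetate 85.05, its trihydrate 139.10 g/mol.

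Amount of substance = 0.350 mmol/ml × 14.2 ml/kg = 4.97 mmol/kg.

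Mass = 4.97 mmol/kg × molar mass / 1000:

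| Mass basis | Implied g/kg | 0.73 ÷ implied | Excess of stated over implied |
|---|---|---|---|
| Sodium d3-acetate, as printed (anhydrous) | 0.423 | 1.727 | 73% |
| Sodium d3-acetate trihydrate (not mentioned) | 0.691 | 1.056 | 5.6% |
| d3-acetate ion only | 0.308 | 2.367 | 137% |

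None of these gives 0.73 at face value.

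**2. Could rounding explain it?**

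The stated mass lies in 0.725-0.735 g/kg and the volume in 14.15-14.25 ml/kg. The answer depends on how 350 mM was rounded, which the documents do not say.

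- To the nearest 10 (345-355 mM): the trihydrate reaches at most 0.355 × 14.25 × 139.10 / 1000 = 0.704 g/kg, short of 0.725.
- To the nearest 50 (325-375 mM): the trihydrate reaches 0.375 × 14.25 × 139.10 / 1000 = 0.743 g/kg, which covers the stated amount.
- For the anhydrous salt, even 375 mM gives only 0.375 × 14.25 × 85.05 / 1000 = 0.454 g/kg. The stated amount is still at least 0.725 / 0.4545 = 1.60 times that.

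Rounding can therefore close the trihydrate gap under a loose convention. It cannot close the gap for the salt as printed.

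**3. Parallel check on the Aim 6 brain infusion.**

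Labelled glucose is a 20% (w/v) solution, 3.6 ml/kg, 0.75 g/kg. 0.20 g/ml × 3.6 ml/kg = 0.72 g/kg, and 0.75 / 0.72 = 1.042, a gap of 4.2%. With 20% rounded to the nearest 1%, 0.205 × 3.65 = 0.748 g/kg, which just reaches the lower bound of 0.745. A gap of about 5% in this section may thus be ordinary approximation.

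**4. D2O.**

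Assumptions not in the documents: body water 40-60% of weight, D2O density 1.107 g/ml.

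- Low: 3 × 0.40 × 1.107 = 1.33 g/kg of weight.
- High: 3 × 0.60 × 1.107 = 1.99 g/kg of weight.
- Against 1-2 mg/kg: widest range 1,328 / 2 = 664 to 1,993 / 1 = 1,993; like for like, 1,328 / 1 = 1,328 (low ends) and 1,993 / 2 = 997 (high ends).

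No body-water fraction in that range brings the two statements together.

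**5. Route.**

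Aim 1 infuses labelled acetate, Aim 3 repeats the Aim 1 method, and Aim 6 infuses labelled glucose and labelled acetate. The oral-only sentence is true of D2O and inulin but not of these. The conflict lies within one paragraph of Minimizing Risks.

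**The case against.** **The acetate gap may be trivial.** If the mass refers to a trihydrate, the difference is 5.6%. A nominal 350 mM could explain it, and it resembles the 4.2% in the glucose figures. This stands: on that reading there may be no error beyond approximation. But it needs a hydration state that the protocol does not give, and on the salt as printed the gap is 73%.

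**Working instructions may be correct.** The pharmacy prepares the solution, and it is infused under an established imaging-centre protocol that is not part of these documents. This also stands. A reader might infer that participants received, or will receive, a wrong acetate dose; the documents do not support that. Nor can the printed figures show which of the three is in error. The Aim 1 acetate rate belongs to a different infusion and does not settle it.

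**The D2O difference looks like mg written for g.** The procedures imply about 1.3-2.0 g/kg and Risks says 1-2 mg/kg, so a unit slip is plausible. The documents do not confirm it, and the text still needs correcting.

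**The infusion risk is covered.** Risks limits its sterility remark to inulin and labelled water, calls acetate infusion low risk and mentions past isotope infusions. This largely stands. A reader might infer that infusion risk was overlooked, but only one sentence is wrong.

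**The cold-isotope condition is template wording.** The confirmation cites no figure from Aim 6 or Risks, and its D2O support refers to the proposed dose, on which Aims 2 and 5 agree. So it would be too strong to call the confirmation invalid. What remains is that it concerns a dose which the protocol does not state consistently, and that the specific support names D2O and inulin, not acetate.

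**Conclusion.** The inconsistency is real and should be fixed. For the Aim 6 liver infusion, concentration times volume gives 4.97 mmol/kg, or 0.42 g/kg for sodium d3-acetate as printed; the stated 0.73 g/kg is about 73% higher. The size depends on the unstated hydration state and mass basis: about 6% for a trihydrate, possibly only rounding, and about 137% for the acetate ion. It rests on standard molar masses, which the documents do not give.

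The D2O statements differ by about 1,000-fold, roughly 660 to 2,000 under the assumed body water and density. The oral-only sentence contradicts the infusions in Aims 1, 3 and 6 and the two sentences after it.

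A reader might grade this as an error that must be fixed before anything else. The documents do not carry it that far: no wrong delivered dose is shown, the acetate gap may be small on one reading, and no endpoint or sample size uses these figures. It is a should-fix. No view is taken on which dose is right.

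**What to change.** In one protocol amendment:

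- Section I, item 4, Aim 6: reconcile the acetate concentration, volume and g/kg amount, and name the form to which the mass refers. Check the glucose figures in the same section.
- Section I, item 10: reconcile the D2O dose and its units with Aims 2 and 5.
- Section I, item 11: correct the oral-only sentence so that it agrees with the infusions in Aims 1, 3 and 6.
- Section II, part B: then check that the cold-isotope dose confirmation refers to the reconciled figures.
- Editorial only: the Aim 6 statistical plan (Section I, item 13) describes the labelled glucose as ingested, while the procedure infuses it; align the wording.

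The cost is a wording amendment and one check with the investigational pharmacy. No procedures, visits or participants are added.
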